6 COLLECTION AND STORAGE OF HUMAN SPECIMENS OR DATA

6.1 Use of samples

Blood samples will be used for:

Research use: samples may be used for future analyses performed either at NIH laboratories or other labs outside NIH (the latter will be pending IRB approval and execution of appropriate agreement). Future research use of these samples includes blood ghrelin levels, GLWL-01 concentrations, biomarkers like feeding-related peptides (e.g., leptin, GLP-1, amylin, GIP, pancreatic polypeptide, PYY, growth hormone (GH), thyroid hormones, insulin, C-peptide, etc.), stress-related hormones (e.g., ACTH, cortisol, etc.) and/or inflammatory markers (e.g., cytokines, etc.), and other biomarkers which may be related to the outcomes of the study. Furthermore, as part of the fully executed CRADA between GLWL Research Inc. and NIH, GLWL Research Inc. may receive de-identified stored blood samples collected in [name] NIH clinical study in order to run biomarkers e.g. blood concentrations of hormones like acyl-ghrelin, UAG and other biomarkers well as blood concentrations of GLWL-01. This latter aspect of the CRADA is planned to generate consistent pharmacokinetic / pharmacogenetic / pharmacodynamic data between [name] clinical study and clinical trials that GLWL Research Inc. is conducting in parallel. The use of the same assays will allow for side-by-side comparison and analysis, therefore providing the best possible information on the role of GLWL-01 on ghrelin signaling across populations affected by different medical disorders.

Clinical use: samples (e.g., glucose, AST, ALT, GGT, bilirubin, creatinine, thyroid and electrolytes) will be analyzed at the Johns Hopkins Bayview Medical Center clinical laboratories or other clinical laboratories approved by the NIDA IRP Clinical Director. In addition to what outlined in the Study Outline, clinical blood labs can be repeated and/or additional clinical labs (blood/urine) may be performed if deemed clinically necessary by the clinicians involved in the study.

6.2 Sample Storage

Electronic data will be stored on the NIDA IRP secure, password-protected electronic medical records system (Clinical Data Warehouse; CDW; Human Research Information System (HuRIS)). Paper records are stored under double lock in an area where individuals who are not part of the study staff do not have access. The existence and types of information contained in the data management system have been publicly reported as required by the FOIA.

Samples not used immediately for clinical reasons will be processed and stored in -80 °C freezers at the NIDA IRP, Baltimore, MD. All biological specimens obtained under this protocol will be stored in coded form (protocol plus subject number) in freezers located an access-controlled area of NIDA.

PI Name: [name]., Ph.D., M.Sc.

Abbreviated Title: GOAT

Version Date: 09/25/2023

7 STATISTICAL ANALYSIS

7.1 *Analysis of data/study outcomes*

Outcome data will be examined for homogeneity of variance, and if necessary transformed to meet this criterion. As this is a within-subjects design, repeated measures analysis of covariance (ANCOVA) will be used to analyze the primary outcome, with drug condition as the within-subjects factor. Similarly, for secondary outcome measures such as food choices, repeated measured ANCOVA will also be used.

Biomarkers and hormonal measurements, such as feeding-related peptides stress-related hormones and/or inflammatory markers (see Section G,1), will also be correlated with changes in primary and secondary outcomes to explore the relationship between hormonal responses of interest and behavioral changes. A probability level of 0.05 or lower will be considered significant.

Potential covariates will be evaluated such that covariates that significantly predict the outcome measure will be retained in the model. Negative affect, as measured by the POMS-2 and Symptom Checklist, and cannabis dependence, if present, will be entered as covariates of particular interest in analysis for primary and secondary outcome responses. Additional covariates include baseline characteristics, like age, race, years of education, alcohol drinking levels, ADS score, family history of alcoholism density and number of days of alcohol abstinence prior to enrollment.

7.2 *Power analysis*

We performed a power analysis for the primary outcome and it is consistent with: 1) our previous Phase 1b study (N = 12 completers) with PF-5190457, where the primary outcome was the number of AEs experienced differ in the drug condition, compared to placebo; and 2) effect sizes ($dz = 0.5$) of alcohol cue-reactivity studies for other medications like the FDA-approved naltrexone and other experimental compounds (George et al., 2008; Miranda et al., 2014; Monti et al., 1999, 2000). The goal will be to reach up to 34 completers. A sample size of 43 subjects will be needed: a) considering the following parameters: $dz = 0.5$, α err prob = .05, and power ($1 - \beta$ err prob) = .80 (see Table 1 for additional details); and b) considering an attrition rate of approximately 20%.

PI Name: [name]., Ph.D., M.Sc.

Abbreviated Title: GOAT

Version Date: 09/25/2023

Table 1: Power Analysis

t tests - Means: Difference between two dependent means (matched pairs)

[figure not shown]
Analysis: A priori: Compute required sample size

Input:

Tail(s)	= Two
Effect size dz	= 0.5
α err prob	= 0.05
Power (1- β err prob)	= 0.8

Output:

Noncentrality parameter δ	= 2.915476
Critical t	= 2.034515
Df	= 33
Total sample size	= 34
Actual power	= 0.807778

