5.2 Design

A within-subject, counterbalanced, double-blind, placebo-controlled study using GLWL-01, in individuals with AUD. Subjects will be randomized to the order of the study drug condition (GLWL-01 and then placebo; or placebo and then GLWL-01) using a block randomization based on the following two variables: sex and smoking status. Associate Investigator [name]., will develop the block randomization grid which will be sent to the NIDA IRP Pharmacy staff. No other members of the study team will have access to the block randomization grid.

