When the participant returns to the CRU after the temporary leave, they will undergo the standard CRU participant search procedure and alcohol and drug screening. A positive BAC or urine drug screen that is positive for any of the following substances: benzodiazepines, barbiturates, cocaine metabolites, morphine, oxycodone, methadone, amphetamine, & buprenorphine may result in an extension of the wash-out window until they are able to provide a negative urine drug screen and or negative BAC or may

PI Name: [name]., Ph.D., M.Sc.

Abbreviated Title: GOAT

Version Date: 09/25/2023

result in termination of study participation and not moving on to the Stage 2 based on the clinical judgement of the PI and MAI. The urine drug screening is identical to the initial drug screen used in the screening procedure and it also includes testing for THC/cannabis however this is not an exclusion criterion nor will it result in termination study. Consistent with the initial drug screening, if cannabis use is detected it will be assessed and entered a covariate in the data analysis. After the inpatient stay, one outpatient follow-up visit in the clinic will be scheduled approximately a week after the discharge (the exact date may vary a little, based on the patient's schedule) to repeat the blood liver panel.

The following research procedures (1-3 listed below) will take place once in Stage 1 and once in Stage 2. These procedures will be the same for Stage 1 and Stage 2. Furthermore, beginning of study procedures may be delayed or participant may be withdrawn from the study for any clinical concerns (for example, clinically relevant severe alcohol withdrawal and/or any other clinical condition requirement immediate medical care).

These study procedures are similar to our ongoing protocol 16-DA-0080, therefore we will be able to compare the potential effects of GLWL-01 versus PF-5190457.

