7.3 Accrual number

Consistent with the within-subject design and other human laboratory studies we and others have performed, we anticipate that approximately 20% of the enrolled participants may not complete the study. Therefore, we anticipate enrolling up to 43 participants in order to reach up to 34 completers.

PI Name: [name]., Ph.D., M.Sc.

Abbreviated Title: GOAT

Version Date: 09/25/2023

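### The two-stage crossover analysis has no Stage (period) term, so any Stage 1 to Stage 2 shift inflates the error, and moves the drug estimate if completers are unequal by order

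*Combined protocol and SAP*

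**What the plan says.** Section 5.2 sets up a two-order crossover: "Subjects will be randomized to the order of the study drug condition (GLWL-01 and then placebo; or placebo and then GLWL-01". Allocation is made "using a block randomization based on the following two variables: sex and smoking status". Section 5.4 (Overview) states that the research procedures, which include cue-reactivity and the virtual buffet, "will take place once in Stage 1 and once in Stage 2".

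For the analysis, section 7.1 states that "repeated measures analysis of covariance (ANCOVA) will be used to analyze the primary outcome, with drug condition as the within-subjects factor", and plans the same kind of model for secondary outcomes such as food choice. Stage is named neither as a factor nor as a covariate. The covariate rule is that "covariates that significantly predict the outcome measure will be retained in the model". Negative affect and cannabis dependence are to be entered, and the list continues: "Additional covariates include baseline characteristics, like age, race, years of education, alcohol drinking levels, ADS score", followed by family history and pre-enrolment abstinence.

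Section 7.2 sizes the trial with a matched-pairs t test (dz = 0.5, two-sided 0.05, 33 df, 34 completers, power 0.807778). Section 7.3 expects that "approximately 20% of the enrolled participants may not complete the study", hence 43 enrolled.

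**The concern.** In a two-period crossover, anything that changes between Stage 1 and Stage 2 for everyone is confounded with treatment within each participant. Counterbalancing makes it cancel on average. It does not remove it from the individual differences, and it cancels exactly only when the two orders have equal numbers of completers.

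A shift is plausible on the protocol's own account. Participants are inpatients for about 14 days with no alcohol given, so Stage 2 falls later in abstinence. Section 3.5 reports that ghrelin rises during abstinence and is associated with craving. Days of abstinence before enrolment is a listed covariate, but it has the same value in both Stages. The cue procedure is repeated, and the virtual buffet needs a training session, so familiarity may also differ.

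The listed baseline covariates are constant within a person and cannot absorb a shift between Stages. At stake are the precision of the drug effect on craving and food choice and, with unequal completers, the estimate itself.

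**Working it through.** **Inputs.** From sections 7.2 and 7.3: n = 34 completers, dz = 0.5, two-sided alpha 0.05, 43 enrolled. Not in the documents, so assumed: a Stage shift p of 0.25, 0.5, 0.75 or 1.0, in units of the SD of the period-free paired difference; completer splits from 17/17 to 20/14; 43 randomised as 22/21. The figures apply to continuous outcomes and are not extended to the adverse-event count.

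**1. The plan's own figure.** Noncentrality = 0.5 × √34 = 2.9155; critical t (33 df) = 2.0345; power = 0.8078. This matches Table 1.

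**2. Model.** Each paired difference is d = τ + p + e in one order and τ − p + e in the other, with e ~ N(0, 1).
- Drug-only analysis: the mean of all d. Its expectation is τ + p(n1 − n2)/n.
- With a Stage term: the average of the two order-specific means. Its expectation is τ for any split, with SE = √[0.25(1/n1 + 1/n2)] and 32 df.

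**3. Equal completers, 17/17.** The expected sample variance of d becomes 1 + p² × 34/33. At p = 0.5 this is 1 + 0.25 × 1.0303 = 1.258, an SD of 1.121. With a Stage term, SE = 0.1715, noncentrality 2.9155, critical t 2.0369 and power 0.807, whatever the shift. The drug-only results come from at least 100,000 simulated trials per scenario.

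Case A takes dz = 0.5 on the period-free SD (τ = 0.5):

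| Shift p | Drug-only power | Power with Stage | Drug-only mean 95% CI width | CI width with Stage | CI wider by | Drug-only type I error |
|---|---|---|---|---|---|---|
| 0.25 | 0.79 | 0.807 | 0.714 | 0.693 | 3% | 0.043 |
| 0.5 | 0.73 to 0.74 | 0.807 | 0.777 | 0.693 | 12% | 0.028 |
| 0.75 | 0.64 | 0.807 | 0.871 | 0.693 | 26% | 0.015 |
| 1.0 | 0.51 | 0.807 | 0.989 | 0.693 | 43% | 0.006 |

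Case B takes dz = 0.5 on an SD that already includes Stage variation (τ = 0.5 × √(1 + p²)):

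| Shift p | Drug-only power | Power with Stage |
|---|---|---|
| 0.25 | 0.81 | 0.83 |
| 0.5 | 0.83 | 0.89 |
| 0.75 | 0.85 | 0.94 |
| 1.0 | 0.88 | 0.98 |

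**4. Unequal completers, case A, p = 0.5, true effect 0.50.** Bias = 0.5 × (n1 − n2)/34.

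| Split | Bias | Drug-only estimate, by direction of shift |
|---|---|---|
| 18/16 | 0.5 × 2/34 = 0.029 | 0.53 or 0.47 |
| 19/15 | 0.5 × 4/34 = 0.059 | 0.56 or 0.44 |
| 20/14 | 0.5 × 6/34 = 0.088 | 0.59 or 0.41 |

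At 19/15, drug-only power is 0.83 or 0.62 depending on the direction of the shift, against 0.80 with a Stage term. Drug-only type I error over these splits, with shifts of 0.25 to 0.5, is 0.03 to 0.05.

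**5. How likely is an unequal split?** If 34 of 43 complete at random from 22/21 (hypergeometric), the gap between orders is 0 with probability 28%, 2 with 44%, and 4 or more with 28%. It is 6 or more with probability 7%.

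**6. Price of the Stage term if there is no Stage effect.** Power goes from 0.8078 to 0.8070 (17/17), 0.806 (18/16), 0.802 (19/15) or 0.795 (20/14).

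**The case against.** The documents show no Stage effect, and every loss above rests on an assumed one. A shift of 1.0 SD is twice the planned drug effect, and at 0.25 SD the loss is negligible. The study also limits shifts by design: identical procedures in both Stages, a water baseline in each cue session, and standardised meals, smoking breaks and meal timing. This stands. It is why the size is given as a range.

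Table 1 is a matched-pairs calculation. On the ordinary reading of dz its SD already contains Stage variation, which is case B, and power does not fall below plan. This also stands: a power shortfall follows only under case A, and the documents do not say which reading is meant.

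The covariate rule is open-ended and could admit Stage. Simulating it (Stage kept only if p < 0.05, 17/17), Stage is retained 29%, 81%, 99% and nearly 100% of the time across the four shifts. Power is then 0.80 to 0.81 and type I error about 0.05. So the rule would work well if Stage were tried, but Stage is not named as a candidate. Whether it is tried would be decided after the data are seen, between two models that give different drug estimates whenever completers are unequal.

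Negative affect and cannabis use may vary between Stages and absorb part of a shift, but neither is a substitute for Stage. Blocking on sex and smoking balances order among those randomised, not among those who complete.

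Finally, the likely bias is small: the gap is 0 or 2 with probability 72%, and at 18/16 with p = 0.5 the bias is 0.03 SD.

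**Conclusion.** The concern holds and should be fixed. The stated model omits a design factor of the crossover. With balanced completers, the drug estimate is unbiased, but the test is conservative and the interval wider than it need be: 12% wider at a shift of 0.5 SD, with a range of 3% to 43% for shifts of 0.25 to 1.0 SD. With unequal completers, the estimate also moves by the shift times (n1 − n2)/n, which is 0.06 SD in either direction at 19/15 and a shift of 0.5. On the random-dropout assumption, an exact 17/17 split has a probability of only 28%.

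No material false-positive inflation is claimed. The sample size in section 7.2 is arithmetically correct on its own terms. Whether power drops below 0.8078 depends on which SD underlies dz. Under either reading, at 17/17 the drug-only analysis has less power than the Stage-adjusted one for each shift examined. The sizes rest on the assumed shifts and splits.

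**What to change.** In section 7.1, add one sentence: Stage (1 or 2) is a pre-specified fixed within-subject effect in the repeated-measures model for cue-elicited craving and for the virtual-buffet outcome, retained whatever its significance. Order may be added too, but with complete pairs it does not change the drug contrast.

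No new data are needed, because Stage is already recorded, and the sample size need not change. The cost is one error degree of freedom: with no Stage effect, power goes from 0.8078 to 0.8070 at 17/17, and to 0.795 at a 20/14 split.

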5.4.7 Additional Considerations

Medication Dose Justification. The dose of 450 mg b.i.d. is consistent with the previous clinical work conducted by the manufacturer GLWL Research Inc.

Missing data. While missing data will be minimized, we do expect that we will not always be able to collect all planned data (an example of a scenario is missing blood samples due to problems with the cannula, hemolysis, and other technical problems; other examples include schedule conflicts including e.g. week-ends, holidays, etc.). Nonetheless, every effort is made to minimize these unforeseen problems with equipment or study procedures. If one should occur, we may ask the participant to repeat a specific experimental procedure (if allowed by the overall study schedule, if it is feasible and if the participant agrees) in order to avoid having to discard other usable data from a participant. Subjects may receive additional compensation if experimental sessions are repeated, consistent with the NIDA Remuneration Policy.

Data sharing with other protocols. Data obtained under this protocol and the NIDA screening protocol may be shared and combined for analysis. This will also allow us to avoid repeating assessments that are scheduled in both protocols during the same period of time, therefore avoiding duplication and minimizing participant fatigue. Participants may also consent for other NIH protocols and data collected under those protocols may be combined with data from this protocol for exploratory purposes.

This protocol does not meet criteria for genomic data sharing. NIH Human Data Sharing (HDS) policy is not applied in this protocol because it is limited by the agreement (CRADA) with GLWL Research Inc.

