10.7 Risk of compensation for tasks

Although we expect that this will be rare, it is possible that being compensated will cause a participant with alcohol dependence to desire to purchase alcohol to such an extent that they will leave the CRU against medical advice. In order to decrease the risk of this, participants will not be paid in cash on the same day of testing.

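### The repeated measures ANCOVA for craving would ordinarily leave out participants with only a Stage 1 session; a mixed model would use their data for a small gain at almost no cost

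*Combined protocol and SAP*

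**What the plan says.** Section 7.1 states that "repeated measures analysis of covariance (ANCOVA) will be used to analyze the primary outcome, with drug condition as the within-subjects factor", and applies the same method to secondary outcomes such as food choices. It adds that "A probability level of 0.05 or lower will be considered significant".

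Table 1 in section 7.2 is a t test headed "Difference between two dependent means (matched pairs"). Its inputs are dz = 0.5, two-sided alpha 0.05 and power 0.80, and it returns 34 participants. Section 7.3 explains the step to 43: "we anticipate that approximately 20% of the enrolled participants may not complete the study". Section 5.4 schedules the cue-reactivity procedure once in each Stage.

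The only text headed as missing data is in section 5.4.7. It deals with failed samples and scheduling, and allows a procedure to be repeated. No section defines an analysis population or says how a participant with Stage 1 data only enters the craving analysis.

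On exits before Stage 2, section 5.4 says that a positive alcohol or drug screen on return from wash-out leave may "result in termination of study participation and not moving on to the Stage 2 based on the clinical judgement" of the investigators; section 5.3 says much the same. Section 10.7 mentions that compensation could make a participant "desire to purchase alcohol to such an extent that they will leave the CRU against medical advice". Section 12 adds withdrawal for adverse events, non-compliance or the participant's own request.

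**The concern.** A repeated measures ANCOVA with one value per condition works on the within-person contrast between drug and placebo. A participant who gives only a Stage 1 value has no contrast, and standard software drops that person. The plan expects about a fifth of participants not to finish, so a valid co-primary measurement could go unused in several of them.

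Two things could be at stake. One is precision: the Stage 1 scores carry some between-person information on the drug effect. The other is selection: if people with high Stage 1 craving were more likely to leave, and the drug lowers craving, more would be lost after placebo first than after drug first, and the remaining pairs would be a selected group. Both need to be sized before deciding how much they matter.

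**Working it through.** **1. The plan's own figure.** For a paired t test with n = 34 and dz = 0.5, the noncentrality is 0.5 × √34 = 2.915, with 33 degrees of freedom and critical t 2.0345. Power is 0.8078, as in Table 1; n = 33 gives 0.795. Enrolment is 34 / 0.80 = 42.5, rounded up to 43. So at most about 43 − 34 = 9 participants fail to complete, and 0.81 is the power after they have been excluded.

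**2. Precision gained by keeping Stage 1-only scores.** Assume compound symmetry with within-person correlation ρ, and 34 pairs and k Stage 1-only participants split equally between sequences. ρ is not in the documents; I vary it from 0.3 to 0.8.

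- Model with drug and Stage: equivalent number of pairs = 34 + k(1 − ρ)/2.
- Model with drug, Stage and sequence: equivalent pairs = 34 ÷ {[(1 + ρ) + (1 − ρ) × 34/(34 + k)]/2}.

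Power uses noncentrality 0.5 × √(equivalent pairs) with 33 degrees of freedom. For ρ = 0.3 and k = 9 without sequence: 34 + 9 × 0.35 = 37.15, noncentrality 3.048, power 0.841.

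| ρ | Pairs, k = 9, no sequence | Power | Pairs, k = 9, with sequence | Power |
|---|---|---|---|---|
| 0.3 | 37.15 | 0.841 | 36.69 | 0.836 |
| 0.5 | 36.25 | 0.832 | 35.88 | 0.828 |
| 0.7 | 35.35 | 0.823 | 35.10 | 0.820 |
| 0.8 | 34.90 | 0.818 | 34.73 | 0.816 |

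Without the sequence term the standard error falls by 1.3% to 4.3%; with it the gain is slightly smaller. If only 5 non-completers have a Stage 1 score, power is 0.813 to 0.827 without the sequence term. Anyone lost before the Stage 1 session adds nothing under either method.

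**3. Bias if dropout depends on the Stage 1 score.** Let the log-odds of dropout be linear in Stage 1 craving. The slopes are assumptions; the documents give none.

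- Dropout set to 9/43, ρ = 0.5, no period effect: odds rising 1.5, 2, 3 or 5-fold per SD shrink the complete-pair estimate by 0.5%, 1.2%, 2.3% and 3.5%. At 5-fold it is 4.9% for ρ = 0.3 and 2.1% for ρ = 0.7.
- Dropout set to 20%, log-odds slopes of 1 to 2 per SD (odds ratios 2.7 to 7.4), ρ from 0.3 to 0.7: about 1% to 6%. At slope 1 and ρ = 0.3, dropout is 16% after drug first and 24% after placebo first.
- Unmodelled period effect, odds rising 1.5 to 5-fold: if Stage 2 craving is 0.3 SD lower, shrinkage reaches 8.6% (5-fold, ρ = 0.3). If it is 0.3 SD higher, the result runs from 1.3% toward zero to 1.5% away from zero.

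In simulation (1,500 trials, ρ = 0.5, 5-fold odds, true effect −0.50), complete pairs averaged −0.478 with power 0.78. The mixed model averaged −0.495 with power 0.82. With no true effect neither method was biased. Rejection rates were then 0.043 (pairs) and 0.060 (mixed model), with Monte Carlo error √(0.05 × 0.95/1,500) = 0.006. The second figure is a reason to require small-sample degrees of freedom.

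**4. Dropout that does no harm.** If exit depends only on a person's stable craving level, that level cancels in the within-person difference. If it depends on craving during wash-out with the drug cleared, simulation with no carryover or period effect gave bias within 0.2% and 20% dropout in both sequences.

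**The case against.** The plan does not state complete-pair deletion. It is inferred from the method named, the single session per Stage and the completer-based sample size. The same team reported a mixed-effects model next to a t test for its earlier crossover (section 3.5), so it may intend one here. That is fair, but section 7.1 does not say so.

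A reader might go further in three ways that the documents do not support.

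- That section 5.4.7 confirms usable data will be thrown away. It says the reverse: a procedure may be repeated "in order to avoid having to discard other usable data from a participant". It sets no analysis rule.
- That entry to Stage 2 depends on craving itself. The gate is a positive alcohol or drug screen after leave that section 5.4 limits to exceptional personal reasons, and a positive screen may instead lengthen the wash-out. Section 10.7 expects departure to buy alcohol to be rare and describes a safeguard.
- That the estimate is pulled toward no effect. This needs exit to follow the Stage 1 score. The leave-related gate operates in a wash-out of at least 2 days, and section 3.7 gives half-lives of 2 to 5.5 hours (across species, not stated for humans). If the drug has cleared, losses through this gate need not differ by sequence.

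It also stands that enrolling 43 already protects planned power when dropout is unrelated to craving, so the gain is an extra and not a repair.

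**Conclusion.** The point holds as a modest improvement to the analysis. Up to about 9 of 43 participants may have a Stage 1 craving score that the named method would ordinarily leave out. Using those scores lifts power from 0.81 to about 0.82 to 0.84 at best, given dz = 0.5, ρ between 0.3 and 0.8 and a usable Stage 1 score in all 9.

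Attenuation is conditional. It is about 1 to 6% if dropout follows the Stage 1 score at the assumed slopes with no period effect, can be larger or reversed with a period effect, and is absent if dropout follows a stable craving level or off-drug wash-out craving. The documents make craving-related exit plausible but give neither its frequency nor its strength. Nothing here threatens the type I error of the paired analysis.

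**What to change.** In section 7.1, analyse craving and virtual-buffet calories with a linear mixed model fitted by REML: drug, Stage and sequence as fixed effects, a random participant effect, and small-sample degrees of freedom (for example Kenward-Roger). Include every randomised participant with at least one session for the outcome concerned. Keep the complete-pair analysis as a sensitivity analysis, and report non-completion by sequence and reason so that readers can judge whether exits differ.

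The cost is SAP wording and slightly more analysis work; no new data or participants are needed and the sample size stays as it is. The downside is that incomplete cases enter under a missing-at-random assumption. Dropout driven by craving that was never recorded would fall outside it, which is why the complete-pair result should be shown alongside.
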